Official Title: An Open, Pared Trial of Recombinant Hepatitis E Vaccine (Escherichia Coli) Hecolin® in the Chronic Hepatitis B Patients on the Clinical Stability. (Aged 30 Years or Over)

NCT number: NCT02964910

Date of the document: June 20, 2018

Brief Study Protocol and Statistical Analysis Plan

Protocol ID: PRO-HE-009

Title: Immunogenicity and safety of Hepatitis E vaccine Hecolin® in persons with chronic hepatitis B: an open-label study in China

Study Dates: Aug, 2016-Dec, 2017

Study Sites: Rushan city, Shandong province, China

Study Objectives

Primary Objectives:

- Evaluate the immunogenicity of the Hepatitis E vaccine in persons with chronic hepatitis B.

Secondary Objectives:

- Evaluate the safety of the Hepatitis E vaccine in persons with chronic hepatitis B.
- Evaluate the safety and immunogenicity of the Hepatitis E vaccine in healthy persons without chronic hepatitis B.

Selection of Study Population

The aim was to enrolled approximately 464 subjects aged ≥ 30 years who were assigned to CHB group and healthy adults group by 1:1. The CHB patients had been diagnosed by clinicians according to the Asian-Pacific clinical practice guidelines before the recruitment.

Inclusion criteria:

all volunteers:

- Aged over 30 years old on the day of enrollment.
- Axillary temperature is below than 37.0°C .
- No administration of hepatitis E vaccine before the study.
- Judged as healthy and eligible for vaccination by the investigators through a self-reported medical history and some physical examinations.
- Able to understand this study information and willing to comply with all study requirements.

- Willing to participate in this study and sign informed consent form.
- Negative serological markers for hepatitis E.

experiment group:

- ALT < 1.5×ULN.
- No spleen swelling, no cirrhosis and no hepatocellular carcinoma.

Exclusion criteria:

- With clinical evidence of malignant tumor.
- History of severe cardio-cerebrovascular disease.
- Administration of hepatotoxicity drugs before or during the study.
- Pregnancy, breast-feeding or plan to be pregnant in 7 months later.
- Participated in any other clinical trial during the study period.
- Use of any investigational product or non-registered product (drug or vaccine) within 30 days preceding the first dose of the study vaccine or plan to use during the study period.
- Received immunosuppressed, immunoregulation therapy or corticosteroid systemic therapy for more than 14 days in the 6 months before entry, except local treatment.
- Administration of any immunoglobulin or blood products within 3 months preceding the first dose of the study vaccine, or plan to use during the study period.
- Administration of any inactivated vaccines within 14 days preceding the first dose of the study or attenuated live vaccines within 21 days preceding the first dose of the study.
- Had a fever (axillary temperature over 38°C) within 3 days or acute illness requiring systemic antibiotics or antiviral treatment within 5 days before vaccination.
- Immunodeficiency (such as HIV carriers), primary disease of important organs, malignant tumor, or any immune disease (such as systemic lupus erythematosus, arthritis pauperum, splenectomy or functional asplenia or other disease which might affect immune response).
- History of allergic disease or history of serious adverse events occurring after vaccination, i.e., allergy, urticaria, dyspnea, angioneurotic edema or abdominal pain.
- Allergic history to any component of this vaccine.
- Asthma that needed emergency treatment, hospitalization, oral or intravenous corticosteroid to keep stable in the past two years.
- Combining another severe internal medicine disease (such as severe hypertension, cardiopathy, diabetes and hyperthyroidism).
- Abnormal coagulation function or coagulopathy diagnosed by doctor.
- Epilepsy (not including alcohol epilepsy within 3 years prior to abstinence and simple epilepsy that do without curing within 3 years prior to the study).
- Abnormal psychology or mind affecting the individual's ability to obey the study requie
- Other medical, psychological, social or occupational factors that, according to the

investigators' judgment, might affect the individual's ability to obey the protocol or sign the informed consent.

Vaccination Schedule

Hecolin® (Xiamen Innovax Biotech Co. Ltd, Xiamen, China) was given intramuscularly to the subjects at day 0, month 1 (+0-30 days) and month 6 (-30-60 days) without any charge. Each dose of vaccine contains 30 µg of the purified antigen adsorbed to 0.8 mg aluminium hydroxide suspended in 0.5 mL buffered saline. All the vaccines have been qualified by China Food and Drug Administration (CFDA) before use.

Safety Assessment

Adverse events (AE) were observed within 30 days after each dose. After each dose, the participants were observed for 30 min for immediate adverse reactions. Within 0-7 days after each dose, the local symptoms at the injection site including pain, red and swollen, pruritus, indurate, and the systematic symptoms including body temperature, allergic reaction, head pain, weakness, nausea, emesis, diarrhea, muscle pain and cough were observed and recorded at the safety diary every day by the participants. AE which happened within 30 days after each dose and drugs and other vaccines administrated were also recorded at the safety diary. All serious adverse events (SAE) were required to report to the researchers within 24 hours during the whole study. The participants who reported AE would be followed up at the end of the study (month 7).

Laboratory Test

Blood samples were obtained from each participant right before the 1st dose (day 0), one month after the 1st dose (at before the 2nd dose, month 1), at before the 3rd dose (month 6) and one month after the 3rd dose (month 7). Five indicators including anti-HEV IgM (only at day 0), anti-HEV IgG, ALT, AST and TBIL were detected in both groups; HBV DNA was detected only in the CHB group. Anti-HEV IgM and IgG was qualitatively detected by ELISA method. Quantitative detection was further conducted for those positive for anti-HEV IgG and the result was expressed in World Health Organization (WHO) units per mL(Wu/mL). The lower limit of anti-HEV IgG quantification was 0.064 Wu/mL. For the analysis, the antibody concentration in samples negative for anti-HEV IgG was arbitrarily set at 0.032 Wu/mL. All reagents for anti-HEV IgG and IgM were supplied by Beijing Wantai Biological Pharmacy Enterprise, Beijing, China and all detections were completed by staffs at Xiamen Innovax Biotech Co. Ltd. ALT and AST were detected by rate method, TBIL was detected by exploring bromocresol green method and HBV DNA was completed by Realtime PCR by the third-party testing organization (ADICON Clinical Laboratories, INC).

Statistical Considerations

Primary endpoints:

- Number of participants whose anti-HEV antibody seroconverted at month 7.

- Geometric mean concentrations of anti-HEV antibody at month 7.

Secondary endpoints:

- Number of participants with changes in liver function index before and one month after the first dose.
- Number of participants with changes in liver function index before and one month after the third dose.
- Number of participants with changes in liver function index before the first dose and one month after the third dose.
- Number of participants who experienced any adverse reactions/events during the whole period of observation (0-7 months).
- Number of participants who experienced solicited adverse reactions/events within 7 days after each vaccination.
- Number of participants who experienced solicited local adverse reactions/events within 7 days after each vaccination.
- Number of participants who experienced solicited system adverse reactions/events within 7 days after each vaccination.
- Number of participants who experienced unsolicited adverse reactions/events within 30 days after each vaccination.
- Number of participants who experienced serious adverse reactions/events during the whole period of observation (0-7 months).

Statistical Analysis Plan

Immunogenicity analysis:

The per-protocol population who met the following criteria was involved in the immunogenicity analysis: 1) satisfied the inclusion criteria for the first dose; 2) without the exclusion condition for the 1st, 2nd and 3rd doses; 3) completed three doses of Hecolin® and blood sample collection at month 7. The immune response was defined as achieving positive anti-HEV IgG at month 7, which was summarized as positive rate and geometric mean concentration (GMC) with 95% confidential intervals (CI) respectively. The difference value of positive rate and GMC ratio of anti-HEV IgG between the CHB group and the control group was calculated with 95%CI. The criteria of the immunogenicity non-inferiority between CHB group and healthy adults group were: 1) the lower limit of 95% CI of the seroconversion rate difference was not less than -10%, and 2) the lower limit of 95%CI of the GMC ratio was not lower than 0.5.

Safety analysis:

The participants who had completed at least one dose of study vaccine and the safety record after the dose were involved in the safety analysis and the participants who went against the protocol after the first dose were not excluded. The reporting rate of AE was calculated and compared by Pearson χ^2 test or Fisher's exact test between the two groups. The effect of hepatitis E vaccination on the liver function was estimated for three times by comparing the value of AST, ALT and TBIL before and one month after the first dose, before and one month after the third dose, before the first dose and one month after the third dose respectively. Changes in the blood test parameters of

ALT, AST and TBIL for each participant were determined by comparing the results of paired blood samples. The fluctuations were classified into three categories: “no change” indicated no grade change; “processed” indicated a change from normal to abnormal or an increase in grade; and “improved” indicated a change from abnormal to normal or a decrease in grade or the change from abnormal to normal. The grade of ALT, AST and TBIL was determined according to the rules issued by China Food and Drug Administration (CFDA). The range of normal value of ALT, AST and TBIL was 0-50 U/L, 0-40 U/L and 2.0-20.4 μ mol/L respectively for males, and was 0-40 U/L, 0-35 U/L and 2.0-20.4 μ mol/L respectively for females.

The data analyses were performed using R software. $P<0.05$ was considered to be statistically significant.

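### The CHB versus healthy-adult non-inferiority verdict rests on a non-randomised comparison, and no age- or sex-adjusted analysis is named beside it

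*Combined protocol and SAP*

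**What the plan says.** **How the groups arise.** Under Selection of Study Population, about 464 people are "assigned to CHB group and healthy adults group by 1:1". The same paragraph makes clear that membership is a pre-existing condition: "The CHB patients had been diagnosed by clinicians according to the Asian-Pacific clinical practice guidelines before the recruitment". Everyone receives the same vaccine. No randomisation or matching is described. Age enters only as a lower limit for eligibility, and sex only through the normal ranges for liver tests under Safety analysis.

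**What is compared.** Under Statistical Analysis Plan, Immunogenicity analysis: "The difference value of positive rate and GMC ratio of anti-HEV IgG between the CHB group and the control group was calculated with 95%CI". In the per-protocol population, non-inferiority requires the lower 95% limit of the rate difference to be at least -10% and that of the GMC ratio to be at least 0.5. No model, covariate, stratum or sensitivity analysis is named.

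**Context.** The official title begins "An Open, Pared Trial of Recombinant Hepatitis E Vaccine". The document describes itself as a "Brief Study Protocol and Statistical Analysis Plan". It carries "Study Dates: Aug, 2016-Dec, 2017" and "Date of the document: June 20, 2018".

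**The concern.** The plan attaches a formal verdict to a contrast between two groups that were not formed by allocation. The comparison is observational in that sense, although vaccination itself is an intervention given to all. Negative hepatitis E serology at entry, a single city and shared exclusions narrow the population, but none of them balances age or sex between the groups. If one group is older or has a different share of women, and if response depends on age or sex, that difference enters the rate difference and the GMC ratio directly. A reader given only the two contrasts could not tell how far a pass or a fail reflects CHB.

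The unexplained word 'Pared' in the official title adds a question. If it means matched participants, an interval for independent groups is not the appropriate one. If it means the before-and-after blood samples described under Safety analysis, it has no bearing on this comparison.

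**Working it through.** No stated figure is in dispute. The check is what an imbalance could do to the verdict.

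**From the documents:** about 464 participants at 1:1, so 232 per group; limits of -10% and 0.5; two-sided 95% intervals; negative samples set at 0.032 Wu/mL against a quantification limit of 0.064 Wu/mL.

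**Assumed, because the documents do not give them:** SD of ln concentration 1.0-1.5; GMC falling by d = 10-20% per decade of age; a 5-year difference in mean age; 180 per group as a smaller per-protocol number.

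**Shift from age.** The shift on the ln scale is -ln(1 - d) × 5/10.
- d = 10%: 0.053, a factor of 1.05.
- d = 20%: 0.112, a factor of 1.12.

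**Standard error.** SE of the ln GMC ratio = SD × √(2/n).
- n = 232: 0.093 (SD 1.0) to 0.139 (SD 1.5).
- n = 180: 0.105 to 0.158.

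**Chance of passing the GMC criterion.** For true ratio R, this is Φ((ln(R/0.5) ± shift)/SE - 1.96). For R = 0.5, SD 1.0 and d = 20%: 0.112/0.0928 - 1.96 = -0.76, which gives 22%. The ranges over SD and d are:

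| True ratio, direction of bias | 232 per group | 180 per group |
|---|---|---|
| 0.5, no bias | 2.5% | 2.5% |
| 0.5, favouring CHB | 6-22% | 5-18% |
| 0.8, against CHB | 73-99% | 62-98% |
| 1.0, against CHB | at least 98.7% | at least 95.7% |

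Without bias, the values at a ratio of 0.8 with 232 per group are 92-99.9%.

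**Sex.** The shift is the difference in the share of women × ln(female/male GMC ratio). With assumed values of 10-20 points and 1.1-1.5, it is 0.010-0.081, a factor of 1.01-1.08. At a true ratio of 0.5 with 232 per group, the chance of passing becomes 3-14%.

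**Both criteria together.** The answer depends on what a halved GMC does to the positive rate.
- *No true rate difference.* Take a control rate of 95% and a bias of +0.5 point. The Wald SE is √(0.95×0.05/232 + 0.955×0.045/232) = 0.0197, and Φ(0.105/0.0197 - 1.96) is about 99.96%. The rate criterion then removes almost nothing, and the joint chance is close to the GMC figure.
- *One lognormal distribution behind both.* Simulate each group with the cut-off at 0.064, negatives at 0.032, 232 per group, a control rate of 95-98% and the same age shifts. The halved GMC lowers the rate by about 3 to 11 points, and the joint chance of a false pass is about 1-17%. At SD 1.0, a control rate of 95% and the larger shift, it is 3%, against 18% for the GMC criterion alone in the same simulation.

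**If participants were matched.** With an assumed within-pair correlation of 0.1-0.3, the independent-groups SE is too large by a factor of 1/√(1 - ρ), that is by 5-20%.

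**The case against.** The strongest reply is that the plan does not claim a causal effect of CHB. The primary objective, "Evaluate the immunogenicity of the Hepatitis E vaccine in persons with chronic hepatitis B", is not worded as a comparison, and the stated contrasts are a valid description of how two groups of vaccinees respond. An adjusted ratio answers a somewhat different question. The documents show no imbalance and no effect of age or sex on response. That the contrasts are unadjusted is inferred from silence, and a document that calls itself brief may have a fuller counterpart. If the true GMC ratio is near 1.0, adjustment would hardly alter the verdict.

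All of this stands, and it limits the point to an improvement. It does not remove the point. The analysis section itself sets non-inferiority criteria between the groups, and the documents give no expected ratio that would show the limit to be far away.

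Three stronger readings are tempting, and the documents support none of them.
- A reader might infer that the comparison is biased or invalid. No size or direction of imbalance is given, so only the possibility is established.
- A reader might take 6-22% as the trial's false-pass rate. It is the GMC criterion alone under assumed inputs. The plan requires both criteria, and the joint figure can be far lower.
- A reader might infer from 'Pared' that participants were matched and the matching was ignored. The only use of 'paired' in the text is for blood samples within a participant, and the title word remains ambiguous.

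**Conclusion.** The point holds as a cheap improvement. The comparison is not randomised and no matching is described, yet a formal verdict is drawn from contrasts for which no covariate or stratum is named. Any age or sex imbalance related to response would be mixed with the CHB effect.

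How much this matters depends on where the true ratio lies. Close to 0.5 a modest imbalance can multiply a nominal 2.5% chance of passing the GMC criterion several times. At 0.8 an adverse imbalance can cost an appreciable share of passes when the SD is large. At 1.0 little changes. These sizes rest on the assumed SD, age or sex effect and imbalance. The joint figures rest also on the assumed link between rate and concentration. The 'Pared' query and the missing description of age and sex by group are matters of detail that would not justify a point by themselves.

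**What to change.** 1. Keep the stated rate difference and GMC ratio, with their limits, as the planned verdict.
2. Beside them, add one labelled sensitivity analysis: the GMC ratio from a linear regression of log month-7 anti-HEV IgG on group, continuous age and sex, with robust standard errors, shown against the unchanged 0.5 limit. Call it post hoc unless outcomes had not been seen when it was specified; the document is in the past tense and dated after the study dates.
3. As an optional secondary check, give a rate difference stratified by sex and age against the unchanged -10% limit.
4. If an adjusted result falls on the other side of its limit, say that the verdict is sensitive to age or sex and do not attribute it to CHB alone.
5. Report age and sex by group. State what 'Pared' means; if participants were matched, name the matching factors and use a confidence interval that accounts for them.

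If a fuller plan already covers this, a reference to it is enough.

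**Cost.** A few sentences, one table and a short analysis in R, the software already named. No new data should be needed, since age is required for eligibility and sex for the liver-test ranges. For a 5-year age gap and an assumed within-group age SD of 8-12 years, the SE grows by 1/√(1 - R²), with R² = 6.25/(6.25 + SD²), which is about 2-5%. The regression carries some model dependence because negatives are set at 0.032 Wu/mL. Unmeasured confounding remains.

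### Month 6 liver tests are never compared with an earlier sample, so a grade rise seen then and back to the day 0 grade or lower by month 7 is not counted as worsening

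*Combined protocol and SAP*

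**What the plan says.** **Sampling.** The Laboratory Test section schedules blood at day 0, at month 1 before dose 2, "at before the 3rd dose (month 6) and one month after the 3rd dose (month 7"). It states that "Five indicators including anti-HEV IgM (only at day 0), anti-HEV IgG, ALT, AST and TBIL were detected in both groups". Only anti-HEV IgM is restricted to day 0, so the three liver tests belong to all four samples.

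**Comparisons.** The Safety analysis section estimates the effect on liver function three times, by comparing values "before and one month after the first dose, before and one month after the third dose, before the first dose and one month after", with dose 3 closing the last pair. In visits these are day 0 to month 1, month 6 to month 7, and day 0 to month 7. Three secondary endpoints match them; the last reads "Number of participants with changes in liver function index before the first dose and one month after the third dose".

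**Categories.** Each pair is classed as *no change*, *processed* (the plan's label for worsening) or *improved*. *Processed* "indicated a change from normal to abnormal or an increase in grade"; *improved* "indicated a change from abnormal to normal or a decrease in grade". The plan describes no worst-grade or any-visit summary.

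**Population.** The safety set needs one dose and the safety record after it, and "the participants who went against the protocol after the first dose were not excluded".

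**The concern.** Month 6 is used only as the starting point for month 7, so a rise that appears there has no earlier sample to be measured against. Where it has settled by month 7, the plan omits the deterioration and records the recovery as an improvement around dose 3. For those participants the error runs in one direction, towards a more favourable picture.

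Safety in chronic hepatitis B (CHB) is the first secondary objective, and the three liver-test comparisons are secondary endpoints. The interval with no planned pair, month 1 to month 6, is the longest between consecutive samples, and month 6 is the only scheduled sample between doses 2 and 3. The primary immunogenicity endpoints and the non-inferiority criteria are not affected.

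**Working it through.** The plan states no figure to reproduce here. The check is one of logic, using the sampling times, the three pairs and the category definitions above.

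**Step 1: pairs used.** Four samples give 4 × 3 / 2 = 6 possible pairs. Three are used, and none ends at month 6.

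**Step 2: the rule.** Write the grades at day 0 and months 1, 6 and 7 as g0, g1, g6, g7, with 0 = normal. Suppose g0 = g1 and g6 > g0.
- Day 0 to month 1 is *no change*.
- Month 6 to month 7 is *processed* only if g7 > g6, which already implies g7 > g0.
- Day 0 to month 7 is *processed* if and only if g7 > g0.

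So a planned pair shows worsening if and only if g7 > g0. If g7 ≤ g0, then g7 < g6, and month 6 to month 7 is scored *improved*.

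**Step 3: enumeration.** The documents do not give the number of grades, so all sequences were listed with 2, 3 and 5 levels. Those with g0 = g1 < g6 number 2, 9 and 50. Worsening is missed in 1, 4 and 20 of them, with no exception to the rule. Adding day 0 to worst post-baseline grade brings the missed count to 0 each time, because g6 > g0 forces the worst grade above g0. These are counts of possible patterns, not probabilities.

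**Step 4: examples.**

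| Grades (day 0, months 1, 6, 7) | Day 0 to month 1 | Month 6 to month 7 | Day 0 to month 7 | Day 0 to worst |
|---|---|---|---|---|
| 0,0,1,0 | no change | improved | no change | processed |
| 1,1,2,1 | no change | improved | no change | processed |
| 0,0,1,1 | no change | no change | processed | processed |
| 0,0,1,missing | no change | none | none | processed |
| 1,0,1,1 | improved | no change | no change | no change |
| 2,0,1,2 | improved | processed | no change | no change |

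The fourth row shows the effect of a missing month 7 sample: two of the three pairs are lost and the month 6 result is used nowhere.

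**Step 5: length of the uncovered interval.** Take 30-day months and read the dose windows in the Vaccination Schedule as +0 to +30 days for dose 2 and -30 to +60 days for dose 3. Dose 2 then falls on days 30 to 60 and dose 3 on days 150 to 240. The gap is nominally 180 - 30 = 150 of 210 days, with a range from 150 - 60 = 90 to 240 - 30 = 210 days. The diary covers the first 30 days after dose 2, which leaves nominally 120 days (60 to 180) outside it.

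**Step 6: illustration only.** The planned 464 participants at 1:1 give 232 per group. If 2% to 10% had a month 6 rise and 25% to 75% of those were back to the day 0 grade or lower by month 7, the rises missed per group would run from 232 × 0.02 × 0.25 = 1.2 to 232 × 0.10 × 0.75 = 17.4. Both ranges are assumptions with no source in the documents.

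**The case against.** The strongest reply is that the plan is coherent as it stands. It compares before with one month after for each dose that has such a sample, plus the whole course. No sample is scheduled one month after dose 2, and a change over a nominal five months could not be ascribed to that dose. On this view a further table is a reporting preference. It is true that the three pairs are sensible and should stay. But the pairs are offered as the estimate of the vaccine's effect on liver function, and following them exactly leaves a recorded rise uncounted.

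A second reply is that other reporting would catch such a rise. SAEs are reported throughout, and any adverse event over 0-7 months is an endpoint. This stands in part. Adverse events are observed for 30 days after each dose, and the documents do not say whether a laboratory grade rise is itself an adverse event. In a document that calls itself brief, that silence proves nothing either way.

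Three stronger readings are tempting and are not supported:
- A reader might infer that every participant with an abnormal month 6 result is reported only as recovering. That is false for 1,0,1,1, where nothing improves around dose 3, and for 2,0,1,2, which is scored *processed* there. Neither ever exceeds the day 0 grade. Nor does it hold when month 7 is missing, since no dose 3 comparison then exists.
- A reader might infer that the secondary endpoints need amending. The study dates end in December 2017 and the document is dated June 20, 2018, so a supplementary analysis is the suitable form.
- A reader might treat HBV DNA as part of the same gap. The plan says "HBV DNA was detected only in the CHB group" and gives no analysis, but it also names no visits for that test. This is at most a separate query about which visits were tested and how results are summarised.

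**Conclusion.** The point holds in limited form. As written, the plan does not count as worsening a month 6 grade rise after equal day 0 and month 1 grades unless month 7 is above day 0. With a month 7 sample at or below the day 0 grade, the only trace is an improvement from month 6 to month 7. With no month 7 sample, the month 6 result enters no comparison, although the safety set is not limited to completers.

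This follows from the stated pairs and categories and needs no assumption about the number of grades. It does rest on reading the liver tests as done at all four samples. Missed here means not counted as worsening in the planned comparisons; the result remains in the data. The number of participants affected is unknown. The change is worth making because it is cheap, not because any effect on the results has been shown.

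**What to change.** In the Safety analysis section, keep the three planned pairs and leave the secondary endpoints as they are. Add one supplementary descriptive summary for ALT, AST and TBIL in both groups: day 0 grade to worst post-baseline grade over months 1, 6 and 7. Use the existing three categories and state how many post-baseline samples each participant has. Label it post hoc if results have been seen. Do not attribute changes to the vaccine or to dose 2, since there is no unvaccinated CHB group.

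A month 1 to month 6 pair is optional. If shown, note that it can score a return to an abnormal day 0 grade as worsening: 1,0,1,1 becomes *processed* although day 0 is never exceeded.

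**Cost.** SAP wording and 3 analytes × 2 groups = 6 more category distributions, on top of the planned 3 × 3 × 2 = 18. No new visit or blood draw is needed. With complete samples, a worst-of-three summary gives at least as many *processed* participants as any single pair starting at day 0. It should therefore be compared between groups only, not with single-pair rates.

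### The liver-function analysis is defined only as a grade shift, so a small general rise in ALT, AST or TBIL could be missed; a paired ratio of values should be added

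*Combined protocol and SAP*

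**What the plan says.** Under Laboratory Test, ALT, AST and TBIL are measured in both groups at day 0 and months 1, 6 and 7. The liver items under Secondary endpoints are counts of people, for example "Number of participants with changes in liver function index before and one month after the third dose".

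The Safety analysis section says the vaccine's effect on liver function is estimated by comparing values over three pairs of visits: day 0 to month 1, month 6 to month 7, and day 0 to month 7. It then defines the outcome: "The fluctuations were classified into three categories". The first category, *no change*, "indicated no grade change". The category printed as *processed* "indicated a change from normal to abnormal or an increase in grade". *Improved* is the reverse.

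For men, "The range of normal value of ALT, AST and TBIL was 0-50 U/L, 0-40 U/L" for ALT and AST respectively; for women the range "was 0-40 U/L, 0-35 U/L and 2.0-20.4". Grades follow external CFDA rules whose cut-points are not given. The section names no mean or median change, ratio, confidence interval or paired test for these values. Its only named tests, chi-square and Fisher's exact, are for adverse event rates between groups.

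**The concern.** The measurements are continuous and paired, which makes them efficient for detecting a change within people. Reducing each pair to three categories discards every movement that does not cross a boundary. Whether a given rise is counted then depends on where the person started: near the limit a trivial change counts, and well below it a large one does not.

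Safety in people with chronic hepatitis B (CHB) is the first secondary objective. A table showing mostly *no change* could be read as evidence that vaccination does not affect the liver, when the table has limited ability to show a small general shift. A comparison between groups does not help, because both are vaccinated and a rise common to both would cancel. By contrast, the plan's Immunogenicity analysis summarises antibody levels as geometric means and a ratio with 95% CI. The same kind of summary is available for the liver values.

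**Working it through.** **Plan's own figure.** The plan states no power or detectable change for the liver endpoints. Its only planning number is about 464 participants at 1:1, so 464/2 = 232 per group. The documents do not give the inputs needed to re-derive 464, and nothing below depends on doing so.

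**Inputs from the documents.** Upper limit of normal (ULN) for ALT: 50 U/L in men, 40 in women. CHB entry: ALT below 1.5×ULN. Significance level: 0.05 (taken as two-sided).

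**Assumptions not in the documents.** Log-normal ALT; male median 22-30 U/L, female median 0.8 times that; between-person log SD 0.35-0.45; within-person log SD 0.20-0.30; grade cuts at 1, 2.5, 5 and 10×ULN; the day-0 value is the entry value.

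**Step 1: what the boundary does (no outside assumption).** A man going from 20 to 49 U/L (49/20 = 2.45-fold) is *no change*. A man going from 49 to 51 (51/49 = 1.04-fold) is *processed*. A doubling stays normal only from 25 U/L or less in men and 20 or less in women.

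**Step 2: individual doublings recorded as *no change*.** Let x be day-0 ALT divided by ULN. Women's assumed median and ULN are both 0.8 times men's, so one calculation serves both sexes. A doubling leaves the category unchanged if x ≤ 0.5, or if 1 < x ≤ 1.25. With F(c) = Φ(ln(c/m)/s), m = median/ULN and s = √(between² + within²):

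share = [F(0.5) + F(1.25) − F(1)] / F(1.5)

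- Median 22 (m = 0.44), s = √(0.35² + 0.20²) = 0.403: (0.624 + 0.995 − 0.979)/0.999 = 64%.
- Median 30 (m = 0.60), s = 0.403: (0.326 + 0.966 − 0.898)/0.989 = 40%.
- Median 30, s = √(0.45² + 0.30²) = 0.541: (0.368 + 0.913 − 0.828)/0.955 = 47%.

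The range is 40-64%, and it is a minority at median 30.

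**Step 3: precision of a paired log ratio.** SE = √2 × within-person SD / √232, which is 0.0186 at SD 0.20 and 0.0279 at SD 0.30. The 95% half-width, 1.96 × SE, is 0.036 to 0.055 on the log scale, or about ±4-6%. For a 10% rise, ln(1.1) = 0.0953, so power is Φ(0.0953/SE − 1.96): Φ(3.17) = 99.9% at SD 0.20 and Φ(1.46) = 93% at SD 0.30.

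**Step 4: group-level power by simulation, n = 232, one interval.** *Processed* against *improved* by an exact sign test, compared with a paired t test on log values:

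| General rise | Grade shift | Paired log ratio |
|---|---|---|
| 10% | about 15-55% | about 92-100% |
| 15% | about 35-90% | about 100% |
| 20% | about 60-99% | about 100% |
| 30% | about 94-100% | about 100% |

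With a single ULN of 45 U/L, between-person SD 0.4 and a lower median of 18 U/L, grade-shift power is 10-16% for a 10% rise, 51-54% for 20% and 89-92% for 30%. Over medians 18-30 in that setting, a general doubling gives about 68-144 *processed* against 0-2 *improved*, with power 100%.

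**Step 5: how the table would look.** In the same single-ULN setting at median 25, the *no change* share is 87-92% with no rise and 85-90% with a general 10% rise, a difference of about 2 percentage points.

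**The case against.** Grade shifts against a regulator's scale are a recognised way to report laboratory safety, and they answer a real question: who becomes abnormal or worsens. The documents set no liver effect size of interest, and a 10% rise (22 to about 24 U/L) is small beside the within-person variation assumed here. The grade-shift power belongs to a test chosen for this review, since the plan names none. The plan is also headed as a brief one, and its statement that values are compared leaves room for a numeric analysis. All of this stands. It supports keeping the shift table and treating the ratio as supplementary. It does not supply the missing estimate, because the sentence on comparing values names no statistic and leads only to the three categories.

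A reader might infer that a doubling of ALT usually disappears. The documents do not support that: they give no baseline distribution, CHB patients are admitted up to 1.5×ULN, and the share falls below half at median 30. A reader might also infer that any modest general rise would probably be missed. That holds near 10%, is mixed at 15%, and fails over the assumed range by 20%, where power is 60% or more.

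**Conclusion.** The concern holds in a limited form. It is certain from the text that a rise crossing no boundary is recorded as *no change*, and that no estimate of numeric change is specified. The consequence is weak sensitivity to a small general shift: about 15-55% power for a 10% rise, against about 92-100% from the same data analysed as paired log values. About 40-64% of individual doublings would not register. Rises of about 30% or more, including a general doubling, would generally be seen at group level.

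These figures rest on the assumed medians, SDs and cut-points and on a test the plan does not name; the direction does not. The point concerns a secondary safety analysis and leaves the primary immunogenicity analysis untouched. It is not evidence that vaccination raises liver enzymes. Nor would the added ratio be the causal effect of the vaccine, since there is no unvaccinated group.

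**What to change.** Keep the shift table and state its grade cut-points. For ALT, AST and TBIL, in each of the three intervals and each group, add:

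- the geometric mean ratio (after/before) with 95% CI, from paired log values;
- the number of participants whose value at least doubled from their own earlier sample.

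Label both as supplementary before/after changes and, since the study dates end in December 2017, as analyses added after data collection. State three limits beside the table:

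- Both groups are vaccinated, so drift over time or in the assay is not separated from a vaccine effect.
- Restricting CHB entry to ALT below 1.5×ULN can produce a small upward regression to the mean, about 0-2%, in intervals starting at day 0 if that sample is the screening value. In simulations with no true rise, a nominal 5% test then rejected in up to roughly 8-10% of trials at the highest assumed median and within-person SD.
- A mean ratio does not describe rare flares, which is why the shift counts must stay.

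The cost is a few lines of SAP wording and one extra table from data already collected. No new samples are needed.
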